1 SYNOPSIS

TITLE: An Open Label Phase II Study of Tipifarnib in Advanced Squamous Non-small Cell Lung Cancer with HRAS mutations

SPONSORS: Fundación GECP

PROTOCOL NUMBER: THOMAS (GECP 17/04)

KURA CODE: KO-IST-003

STUDY SITES: 30 centers in Spain

PHASE OF DEVELOPMENT: Phase II

STUDY PERIOD: This trial is planned to initiate enrolment in the first half of 2017. It is estimated that it may require approximately 3 years to complete all its study objectives.

OBJECTIVES:

Primary Objective: To determine the antitumor activity in terms of objective response rate (ORR) of tipifarnib in subjects with locally advanced unresectable or metastatic, relapsed and/or refractory, squamous non-small cell lung cancer (SQ-NSCLC) with HRAS mutations. This objective will be evaluated in the treatment phase of the study.

Secondary Objective 1: To determine the frequency of HRAS mutations in squamous non-small cell lung cancer (SQ-NSCLC). This objective will be evaluated in the pre-screening phase of the study.

Secondary Objective 2: Safety and tolerability of tipifarnib in subjects with locally advanced unresectable or metastatic, relapsed and/or refractory, squamous non-small cell lung cancer (SQ-NSCLC) with HRAS mutations. This objective will be evaluated in the treatment phase of the study.

Exploratory Objective 1: To explore the antitumor activity in terms of progression free survival (PFS) and duration of response (DOR) of tipifarnib in subjects with locally advanced unresectable or metastatic, relapsed and/or refractory, squamous non-small cell lung cancer (SQ-NSCLC) with HRAS mutations. This objective will be evaluated in the treatment phase of the study.

Exploratory Objective 2: To explore the identification of biomarkers potentially related to tipifarnib activity in tumor tissue and/or cell free DNA. This objective will be evaluated in the treatment phase of the study.

STUDY DESIGN:

This Phase II study consists of 2 parts: 1) pre-screening phase and 2) treatment phase.

The pre-screening phase will investigate the presence of HRAS mutations in subjects with a histologically or cytologically confirmed diagnosis of squamous non-small cell lung cancer (SQ-NSCLC). Subjects may participate in the pre-screening phase at initial diagnosis or following prior lines of therapy for SQ-NSCLC.

The treatment phase will investigate the antitumor activity in terms of ORR of tipifarnib in subjects with locally advanced squamous non-small cell lung cancer (SQ-NSCLC) with HRAS mutations and for whom there is no curative therapy available. Subject enrolment may proceed with information available on tumor HRAS status previously generated during the pre-screening phase, but all subjects must consent to provide tumor slides (or tumor tissue block) from a prior diagnostic biopsy for a retrospective testing of RAS gene status, including T81C polymorphism, and other potential biomarkers at a central facility.

Tipifarnib will be administered at a starting dose of 600 mg, po, bid daily on days 1-7 and 15-21 of 28-day treatment cycles. In the absence of unmanageable toxicities, subjects may continue to receive tipifarnib treatment for up to 24 months in the absence of disease progression and unmanageable toxicity. Treatment may continue beyond 24 months if there is documented evidence of continued clinical benefit.

Tumor assessments will be performed at screening and approximately every 8 weeks for the first 6 months (cycles 2, 4, 6) and then every 12 weeks (cycles 9, 12, 15, etc.) until disease progression, starting at the end of Cycle 2. Additional tumor assessments may be conducted if deemed necessary by the Investigator or for a confirmation of an objective response. Subjects who discontinue tipifarnib treatment for reasons other than disease progression must continue tumor assessments until disease progression, withdrawal of subject's consent to study procedures or initiation of another anticancer therapy.

Determination of objective tumor response will be performed by the Investigator according to the Response Evaluation Criteria in Solid Tumors (RECIST) v 1.1 (Appendix II). Electronic copies of tumor images may be de-identified of subject's personal information at the clinical sites and collected by the Sponsor to undergo an external independent radiological review if the sponsor deems it necessary for the final assessment of treatment efficacy. Subjects with a solitary site of disease who have experienced a response may be considered for surgical resection. Subjects with a best response of a partial response and residual disease after salvage surgery will be eligible to continue on study therapy. Information on the duration of response to the last prior therapy will be collected.

Upon disease progression, subjects will be followed approximately every 12 weeks for survival until either death or 24 months after accrual in the subject's study cohort has been completed, whichever occurs first. Information on subsequent anticancer therapy will be collected.

All subjects will be followed-up for safety during treatment and for approximately 30 additional days after treatment discontinuation (or until immediately before the administration of another anticancer treatment). Additional safety follow up may be conducted if unresolved toxicity is present at the End of Treatment visit.

NUMBER OF SUBJECTS PLANNED: It is anticipated that approximately 2000 subjects will be enrolled in the pre-screening phase and up to 18 evaluable study subjects in the treatment phase.

SUBJECT SELECTION:

Inclusion Criteria

For inclusion of a subject in the pre-screening phase, all of the following inclusion criteria must be fulfilled:

- 1. Subject is at least 18 years of age.
- 2. Subject has a histologically or cytologically confirmed diagnosis of squamous non-small cell lung cancer (SQ-NSCLC).
- Subject has consented to provide either a blood sample, tumor slides or tumor tissue blocks (including a fresh biopsy if no archival material is available) for testing of HRAS gene tumor status, including mutations, estimated amplification and T81C polymorphism status.
- 4. Written and voluntary informed consent for the pre-screening phase understood, signed and dated.

For inclusion of a subject in the treatment phase, all of the following inclusion criteria must be fulfilled:

- 1. Subject has a histologically or cytologically confirmed diagnosis of squamous non-small cell lung cancer (SQ-NSCLC) for which there is no curative therapy available.
- 2. Subject has relapsed (progressive disease) or is refractory to one or more prior therapies. In the case of therapy received in the adjuvant or neo-adjuvant setting, relapse must have occurred within 12 months to be considered prior therapy. Subject may have received prior immunotherapy.

- 3. Subject has a tumor that carries a missense HRAS mutation. HRAS status may have been assessed either in blood, primary tumor tissue, recurrent or metastatic disease.
- 4. Subject has consented to provide tumor slides (or tumor tissue blocks) for biomarker evaluation. Before enrolment the site must confirm the availability of the tumor sample. If there is no sample available, the trial chair must be contacted for approval. If enrolment in the treatment portion of the study has taken place based on HRAS mutant status as assessed using a blood sample, tumor tissue must be sent before starting cycle 2 of treatment, and It will be used in part for confirmation of HRAS mutant tumor status. Confirmation of HRAS mutant status in tumor tissue is required for continuation of treatment. If HRAS mutant is not confirmed in tumor but is clearly positive in blood, the trial chair will be contacted for approval and the treatment could be maintained. All treated subjects will be evaluated for safety.
- 5. Subject has measurable disease according to RECIST v1.1.
- 6. At least 2 weeks since the last systemic therapy regimen prior to enrolment. Subjects must have recovered to NCI CTCAE v. 4.03 < Grade 2 from all acute toxicities (excluding Grade 2 toxicities that are not considered a safety risk by the Sponsor and Investigator) or toxicity must be deemed irreversible by the Investigator.

- 7. At least 2 weeks since last radiotherapy. If radiation was localized to the only site of measurable disease, there must be documentation of disease progression of the irradiated site. Subjects must have recovered from all acute toxicities from radiotherapy. Subjects may be on a daily dose of corticosteroids (≤ 20mg prednisone or equivalent), as part of their management from prior radiotherapy.
- 8. ECOG performance status of 0 or 1.
- 9. Acceptable liver function:
 - a. Bilirubin \leq 1.5 times upper limit of normal (x ULN); does not apply to subjects with Gilbert's syndrome diagnosed as per institutional guidelines.
 - b. AST (SGOT) and ALT (SGPT) \leq 3 x ULN; if liver metastases are present, then \leq 5 x ULN is allowed.
- 10. Acceptable renal function with serum creatinine \leq 1.5 x ULN or a calculated creatinine clearance \geq 60 mL/min using the Cockcroft-Gault or MDRD formulas.
- 11. Acceptable hematologic status:
 - a. ANC \geq 1000 cells/µL.

- b. Platelet count \geq 75,000/µL.
- c. Hemoglobin \ge 9.0 g/dL.
- 12. Female subjects must be:
 - a. Of non-child-bearing potential (surgically sterilized or at least 2 years postmenopausal); or

If of child-bearing potential, subject must use an adequate method of contraception consisting of two-barrier method or one barrier method with a spermicide or intrauterine device. Both females and male subjects with female partners of child-bearing potential must agree to use an adequate method of contraception for 2 weeks prior to screening, during, and at least 4 weeks after last dose of trial medication. Female subjects must have a negative serum or urine pregnancy test within 72 hours prior to start of trial medication.

- b. Not breast feeding at any time during the study.
- 13. Written and voluntary informed consent for the treatment phase understood, signed and dated.

Exclusion Criteria

The subject will be **excluded from participating in the pre-screening phase** if any of the following criteria are met:

- 1. Concomitant disease or condition that could interfere with the conduct of the study, or that would, in the opinion of the Investigator, pose an unacceptable risk to the subject in this study.
- 2. The subject has legal incapacity or limited legal capacity.
- 3. Significantly altered mental status that would limit the understanding or rendering of informed consent and compliance with the requirements of this protocol. Unwillingness or inability to comply with the study protocol for any reason.

The subject will be **excluded from participating in the treatment phase** if any of the following criteria are met:

- 1. Ongoing treatment with an anticancer agent not contemplated in this protocol.
- 2. Prior treatment (at least 1 full treatment cycle) with an FTase inhibitor.
- 3. Any history of clinically relevant coronary artery disease or myocardial infarction within the last 3 years, New York Heart Association (NYHA) grade III or greater congestive heart

failure, cerebro-vascular attack within the prior year, or current serious cardiac arrhythmia requiring medication except atrial fibrillation.

- 4. Known uncontrolled brain, leptomeningeal or epidural metastases (unless treated and well controlled for at least 4 weeks prior to Cycle 1 Day 1).
- 5. Non-tolerable ≥ Grade 2 neuropathy or evidence of emerging or rapidly progressing neurological symptoms within 4 weeks of Cycle 1 Day 1. Non-tolerable grade 2 toxicities are defined as those with moderate symptoms that the patient is not able to endure for the conduct of instrumental activities of daily life or that persists ≥ 7 days.
- 6. Major surgery, other than diagnostic surgery, within 4 weeks prior to Cycle 1 Day 1, without complete recovery.
- 7. Active, uncontrolled bacterial, viral, or fungal infections, requiring systemic therapy. Known infection with HIV, or an active infection with hepatitis B or hepatitis C.
- 8. Subjects who have exhibited allergic reactions to tipifarnib or structural compounds similar to tipifarnib or to the drug product excipients. This includes hypersensitivity to imidazoles, such as clotrimazole, ketoconazole, miconazole and others in this drug class. Patients with hypersensitivity to these agents will be excluded from enrolment.
- 9. Required use of concomitant medications classified as strong inhibitors or inducers of cytochrome P450 3A4 (CYP3A4, Table 4) or UDP-glucuronosyltransferase (UGT).
- 10. Concomitant disease or condition that could interfere with the conduct of the study, or that would, in the opinion of the Investigator, pose an unacceptable risk to the subject in this study.
- 11. The subject has legal incapacity or limited legal capacity.
- 12. Significantly altered mental status that would limit the understanding or rendering of informed consent and compliance with the requirements of this protocol. Unwillingness or inability to comply with the study protocol for any reason.

STATISTICAL METHODS:

Descriptive statistics are planned for the pre-screening phase. The sample size was determined based on the expected frequency of HRAS mutations in SQ-NSCLC (~2%). In order to identify up to 18 evaluable subjects that could enroll into the treatment phase, approximately 2000 subjects will be enrolled in the pre-screening phase.

Up to 18 evaluable subjects will be enrolled in the treatment phase using a two-stage design (Simon, 1989). Evaluable subjects are those that have HRAS missense mutant status in a tissue

sample, have an available baseline scan, and have received at least one daily administration (2 doses) of tipifarnib. Seven evaluable study subjects will be enrolled for the first stage; the study will be terminated if 0 responses are observed at end of first stage. Otherwise, an additional 11 subjects will be enrolled for the second stage.

At the completion of two-stage study, the study is considered as failure if there are 3 or less responses out of 18 evaluable subjects, indicating the true ORR is 10% or less. If there are 4 or more responses, the treatment will be considered of further interest indicating the true ORR is higher than 10%.

For this two-stage study design, a null response rate of 10% and alternative response rate of 30% are assumed. It provides 80% power to detect a difference between 10% and 30% ORR at one-sided significance level of 0.089. Using this design, the probability of terminating the study at the end of first stage is 0.48 if the true ORR is 10% or less while the probability of terminating the study at the study at the end of first stage is 0.13 if the true ORR is 30%.

Summary statistics will be provided for other endpoints.

Table 1: Schedule of Activities

	PRF-		Т	REATME	NT PHAS	E	End of		
Activity	SCREENING PHASE	Screening	D1 (± 2d) ³	D8 (± 2d) ³	D15 (± 2d) ³	D22 (± 5d)4	Treatment Visit ⁵	Follow Up Visit ⁶	Follow Up Contact ⁶
ICF for pre-screening, Inclusion/exclusion criteria evaluation	x								
HRAS mutation testing ¹	х								
ICF for treatment phase, Inclusion / exclusion criteria evaluation, Collection of HRAS mutation information		x							

14 of 89

15 of 89

3 ABBREVIATIONS

AE	Adverse event
AKT	Serine/Threonine kinase AKT
ALT	Alanine Aminotransferase
ANC	Absolute neutrophil count
APTT	Activated partial thromboplastin time
ASaT	All subjects as treated
AST	Aspartate Aminotransferase
AUC	Area under the curve
bid	Twice a day
BSC	Best supportive care
BUN	Blood urea nitrogen
Cmax	Maximum concentration
Cmin	Minimum concentration
CBC	Complete blood count
CEA	Carcinoembryonic antigen
CFR	Code of federal regulations
CR	Complete response
CRF	Case report form
CSR	Clinical study report
СТ	Computer tomography
CTCAE	Common Terminology Criteria for Adverse Events
DLT	Dose limiting toxicity
DOR	Duration of response
DPA	Data protection act
DTC	Differentiated thyroid cancer
ECG	Electrocardiogram
ECOG	Eastern cooperative oncology group
ERK	Extracellular signal-regulated kinase
EU	European Union
FAS	Full analysis set
FDA	Food and Drug Administration
FFPE	Formalin-fixed, paraffin-embedded
FTase	Farnesyl transferase
GCP	Good Clinical Practice
HIPAA	Health Insurance Portability and Accountability Act
HIV	Human immunodeficiency virus
HNSCC	Head and neck squamous cell carcinoma
HPV	Human Papilloma Virus
HRAS	Harvey rat sarcoma virus gene homolog

IB	Investigator's brochure
ICF	Informed consent form
ICH	International Conference on Harmonization
IEC	Independent Ethics Committee
INR	International normalized ratio
IP	Investigational product
IRB	Institutional Review Board
IV	Intravenous
KRAS	Kirsten rat sarcoma virus gene homolog
MDRD	Modification of the diet in renal disease
MDS	Myelodysplastic syndromes
MeDRA	Medical Dictionary for Regulatory Activities
MRI	Magnetic resonance imaging
MSKCC	Memorial Sloan Kettering Cancer Center
MTC	Medullary thyroid cancer
NCI	National Cancer Institute
NSCLC	Non-small cell lung cancer
NYHA	New York Heart Association
ORR	Objective response rate
PD	Progressive disease
PE	Physical examination
PFS	Progression free survival
PI	Principal Investigator
PIC	Patient informed consent
РК	Pharmacokinetic
PR	Partial response
PT/INR	Prothrombin time/international normalized ratio
RECIST	Response evaluation criteria in solid tumors
SAE	Serious adverse event
SAP	Statistical analysis plan
SCLC	Small cell lung cancer
SD	Stable disease
SGOT	Serum glutamic oxaloacetic transaminase
SGPT	Serum glutamic pyruvic transaminase
SUSAR	Suspected Unexpected Serious Adverse Reactions
T1/2	Half-life
TEAE	Treatment-emergent adverse event
Tmax	Time to maximum concentration
TSH	Thyroid stimulating hormone
ULN	Upper limit of normal
V	Version

4 INTRODUCTION

Beginning in 1997, tipifarnib was the first specific inhibitor of farnesyl transferase (FTase) to enter clinical studies and has been evaluated in over 70 clinical oncology and hematology studies.

Brief information on tipifarnib is presented in this section; more extensive information is provided in the Investigator's Brochure (Tipifarnib Investigator's Brochure, Edition 15, January 2019).

24 of 89

5 OBJECTIVES

5.1 **Primary Objectives and Endpoints**

Primary Objective: To determine the antitumor activity in terms of objective response rate (ORR) of tipifarnib in subjects with locally advanced unresectable or metastatic, relapsed and/or

refractory, squamous non-small cell lung cancer (SQ-NSCLC) with HRAS mutations. This objective will be evaluated in the treatment phase of the study.

Primary endpoint: Response assessments according to RECIST 1.1.

5.2 Secondary Objectives and Endpoints

Secondary Objective 1: To determine the frequency of HRAS mutations in squamous non-small cell lung cancer (SQ-NSCLC). This objective will be evaluated in the pre-screening phase of the study.

Secondary Endpoint 1: Molecular analyses of tumor and/or cell free DNA samples.

Secondary Objective 2: Safety and tolerability of tipifarnib in subjects with locally advanced unresectable or metastatic, relapsed and/or refractory, squamous non-small cell lung cancer (SQ-NSCLC) with HRAS mutations. This objective will be evaluated in the treatment phase of the study.

Secondary Endpoint 2: Treatment-emergent adverse events (TEAE) and SAEs evaluated according to NCI CTCAE v.4.03.

5.3 Exploratory Objective and Endpoints

Exploratory Objective 1: To explore the antitumor activity in terms of progression free survival (PFS) and duration of response (DOR) of tipifarnib in subjects with locally advanced unresectable or metastatic, relapsed and/or refractory, squamous non-small cell lung cancer (SQ-NSCLC) with HRAS mutations. This objective will be evaluated in the treatment phase of the study.

Exploratory Endpoints 1: PFS and DOR according to RECIST 1.1.

Exploratory Objective 2: To explore the identification of biomarkers potentially related to tipifarnib activity in tumor tissue and/or cell free DNA. This objective will be evaluated in the treatment phase of the study.

Exploratory Endpoints 2: Molecular analyses of archival tissue samples.

6 SUBJECT SELECTION

6.1 Inclusion Criteria

6.1.1 Pre-screening Phase

For inclusion of a subject in the pre-screening phase, all of the following inclusion criteria must be fulfilled:

- 1. Subject is at least 18 years of age.
- 2. Subject has a histologically or cytologically confirmed diagnosis of squamous non-small cell lung cancer (SQ-NSCLC).
- 3. Subject has consented to provide either a blood sample, tumor slides or tumor tissue blocks (including a fresh biopsy if no archival material is available) for testing of HRAS gene tumor status, including mutations, estimated amplification and T81C polymorphism status.
- 4. Written and voluntary informed consent for the pre-screening phase understood, signed and dated.

6.1.2 Treatment Phase

For inclusion of a subject in the treatment phase, all of the following inclusion criteria must be fulfilled:

- 1. Subject has a histologically or cytologically confirmed diagnosis of squamous non-small cell lung cancer (SQ-NSCLC) for which there is no curative therapy available.
- Subject has relapsed (progressive disease) or is refractory to one or more prior therapies. In the case of therapy received in the adjuvant or neo-adjuvant setting, relapse must have occurred within 12 months to be considered prior therapy. Subject may have received prior immunotherapy.
- 3. Subject has a tumor that carries a missense HRAS mutation. HRAS status may have been assessed either in primary tumor tissue, recurrent or metastatic disease.
- 4. Subject has consented to provide tumor slides (or tumour tissue blocks) for biomarker evaluation. Before enrolment the site must confirm the availability of the tumor sample. If there is no sample available, the trial chair must be contacted for approval. If enrolment in the treatment portion of the study has taken place based on HRAS mutant status as

assessed using a blood sample, tumor tissue must be sent before starting cycle 2 of treatment, and It will be used in part for confirmation of HRAS mutant tumor status. Confirmation of HRAS mutant status in tumor tissue is required for continuation of treatment. If HRAS mutation is not confirmed in tumor but is clearly positive in blood, the trial chair will be contacted for approval and the treatment could be maintained. All treated subjects will be evaluated for safety.

- 5. Subject has measurable disease according to RECIST v1.1.
- 6. At least 2 weeks since the last systemic therapy regimen prior to enrolment. Subjects must have recovered to NCI CTCAE v. 4.03 < Grade 2 from all acute toxicities (excluding Grade 2 toxicities that are not considered a safety risk by the Sponsor and Investigator) or toxicity must be deemed irreversible by the Investigator.

- 7. At least 2 weeks since last radiotherapy. If radiation was localized to the only site of measurable disease, there must be documentation of disease progression of the irradiated site. Subjects must have recovered from all acute toxicities from radiotherapy. Subjects may be on a daily dose of corticosteroids (≤ 20mg prednisone or equivalent), as part of their management from prior radiotherapy.
- 8. ECOG performance status of 0 or 1.
- 9. Acceptable liver function:
 - a. Bilirubin \leq 1.5 times upper limit of normal (x ULN); does not apply to subjects with Gilbert's syndrome diagnosed as per institutional guidelines.
 - b. AST (SGOT) and ALT (SGPT) \leq 3 x ULN; if liver metastases are present, then \leq 5 x ULN is allowed.
- 10. Acceptable renal function with serum creatinine \leq 1.5 x ULN or a calculated creatinine clearance \geq 60 mL/min using the Cockcroft-Gault or MDRD formulas.
- 11. Acceptable hematologic status:
 - a. ANC \geq 1000 cells/µL.
 - b. Platelet count \geq 75,000/µL.
 - c. Hemoglobin \geq 9.0 g/dL.
- 12. Female subjects must be:
 - a. Of non-child-bearing potential (surgically sterilized or at least 2 years postmenopausal); or

If of child-bearing potential, subject must use an adequate method of contraception consisting of two-barrier method or one barrier method with a spermicide or intrauterine device. Both females and male subjects with female partners of child-bearing potential must agree to use an adequate method of contraception for 2 weeks prior to screening, during, and at least 4 weeks after last dose of trial medication. Female subjects must have a negative serum or urine pregnancy test within 72 hours prior to start of trial medication.

- b. Not breast feeding at any time during the study.
- 13. Written and voluntary informed consent for the treatment phase understood, signed and dated.

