11.3 Sample Size Determination

No statistical testing is planned for the pre-screening phase. The sample size was determined based on the expected frequency of HRAS mutations in SQ-NSCLC (2%). In order to identify up to 18 evaluable subjects that could enroll into the treatment phase, approximately 2000 subjects will be enrolled in the pre-screening phase.

Up to 18 evaluable subjects will be enrolled in the treatment phase using a two-stage design (Simon, 1989). Seven evaluable study subjects will be enrolled for the first stage; the study will

be terminated if 0 responses are observed at end of first stage. Otherwise, an additional 11 subjects will be enrolled for the second stage.

At the completion of two-stage study, the study is considered as failure if there are 3 or less responses out of 18 evaluable subjects, indicating the true ORR is 10% or less. If there are 4 or more responses, the treatment will be considered of further interest indicating the true ORR is higher than 10%.

For this two-stage study design, a null response rate of 10% and alternative response rate of 30% are assumed. It provides 80% power to detect a difference between 10% and 30% ORR at one-sided significance level of 0.089. Using this design, the probability of terminating the study at the end of first stage is 0.48 if the true ORR is 10% or less while the probability of terminating the study at the study at the end of first stage is 0.13 if the true ORR is 30%.

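### For blood-enrolled subjects, the tissue result that defines evaluability is due only after dosing starts, so early failures whose tissue is never tested can leave the 7/18 count

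*Combined protocol and SAP*

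**What the plan says.** Section 11.3 sets the design: "Up to 18 evaluable subjects will be enrolled in the treatment phase using a two-stage design". The Synopsis gives the first stage: "Seven evaluable study subjects will be enrolled for the first stage; the study will be terminated if 0 responses are observed". Section 11.3 continues: "Otherwise, an additional 11 subjects will be enrolled for the second stage". At the end, "the study is considered as failure if there are 3 or less responses out of 18 evaluable subjects".

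Evaluability is defined only in the Synopsis, under Statistical Methods: "Evaluable subjects are those that have HRAS missense mutant status in a tissue" sample, who also have a baseline scan and have taken two doses of tipifarnib. The definition asks for no scan after baseline and sets no time limit on the tissue result.

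The Synopsis accepts an HRAS result from blood for entry. In Section 6.1.2, criterion 3 does not mention blood, but criterion 4 provides for it: the site confirms before enrolment that a tumour sample exists, and for a blood-enrolled subject "tumor tissue must be sent before starting cycle 2 of treatment". Criterion 4 also has an exception: "If there is no sample available, the trial chair must be contacted for approval". Tissue confirmation is a condition for continuing treatment, unless the trial chair agrees otherwise for a subject clearly positive in blood.

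Section 9.1 places the first scheduled on-treatment tumour assessment at the end of cycle 2. Section 11.1.1 makes the FAS, not the evaluable set, the primary population for tumour response. The FAS has no tissue condition, but it leaves out subjects with no endpoint data after baseline.

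**The concern.** For blood-enrolled subjects, one condition for being counted in the 7 and the 18 is settled after treatment begins. A subject who dies, progresses or stops within the first 28-day cycle never reaches the shipping deadline. Because tissue confirmation is tied to continuing treatment, stopping also removes the practical reason to obtain it. The available text does not say that such a subject's tissue must still be tested, or how a missing result counts.

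Any loss at that point is one-sided. The first scheduled response scan comes a cycle later, so nearly everyone lost would be a non-responder. The rate among evaluable subjects would then exceed the rate among treated subjects. If enrolment continued until 18 evaluable subjects were reached, the 10% null and the 0.089 error rate would no longer describe the treated population. The study is open label with investigator-assessed response, and the available text does not say that evaluability is decided without knowledge of outcome.

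**Working it through.** **Inputs.** From Section 11.3: n1 = 7, stop at 0 responses; n = 18, success at 4 or more; "a null response rate of 10% and alternative response rate of 30% are assumed"; one-sided alpha 0.089, power 80%, probability of stopping after stage 1 of 0.48 at a response rate of 10%. The documents give no blood-enrolled share and no rate of loss in cycle 1, so both are assumed below.

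**Step 1: the plan's own figures.**

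P(stop after stage 1) = (1 − p)^7, which is 0.9^7 = 0.478 at p = 0.10.

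P(success) = Σ over x = 1 to 7 of C(7,x) p^x (1 − p)^(7−x) × P[Bin(11, p) ≥ max(0, 4 − x)].

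At p = 0.10:

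- x = 1: 0.3720 × 0.0896 = 0.0333
- x = 2: 0.1240 × 0.3026 = 0.0375
- x = 3: 0.0230 × 0.6862 = 0.0158
- x ≥ 4: 0.0027
- Sum: 0.0893

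At p = 0.30 the same sum is 0.8000. The stated alpha, power and 0.48 all reproduce. The stated 0.13 for stopping at a response rate of 30% does not (0.7^7 = 0.082). That is a separate matter and does not affect what follows.

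**Step 2: loss with replacement.** Let B be the share of treated subjects enrolled on blood, and E the share of those who fail in cycle 1 and never get a tissue result. Then d = B × E is the share of all treated subjects lost. If all of them are non-responders and all are replaced, the response rate among evaluable subjects is p/(1 − d). Putting that rate through the formula in Step 1, with a true rate of 10% among treated subjects:

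| Example B × E | d | Evaluable rate 0.10/(1 − d) | Alpha |
|---|---|---|---|
| none lost | 0 | 10.0% | 0.089 |
| 10% × 10% | 1% | 10.1% | 0.092 |
| 25% × 20% | 5% | 10.5% | 0.103 |
| 50% × 20% | 10% | 11.1% | 0.120 |
| 100% × 20% | 20% | 12.5% | 0.165 |

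Alpha passes 0.10 at d of about 4%. In expectation that is 18/0.96 − 18 = 0.75 of a replaced subject.

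**Step 3: loss without replacement.** The lost subjects are non-responders, so the number of responses does not change and the rule of 4 or more is not inflated. Only the reported percentage rises.

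**Step 4: effect on the reported rate.** With 4 responses, the evaluable rate is 4/18 = 22.2%. Counting one lost subject gives 4/19 = 21.1%; counting two gives 4/20 = 20.0%.

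**Step 5: after the fix.** If every treated subject counts in the 7 and the 18, with a missing result taken as non-response, p is the rate among treated subjects. Step 1 then applies unchanged: alpha 0.0893, power 0.8000. Removing subjects on a tissue result obtained for everyone, whatever their outcome, would not bias the rule either.

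**The case against.** A reader might infer that membership of the denominator depends on surviving cycle 1. The documents do not support that. The evaluable definition sets no date for the tissue result. The tissue comes from an earlier diagnostic biopsy, all subjects consent to its retrospective testing (Section 7.1), and the site confirms before enrolment that it exists. The start of cycle 2 is the latest shipping date, and a stored block can be tested after a subject has stopped or died. An early failure drops out only if the tissue is never sent or tested. This answers the strong reading. It leaves open that the available text permits late testing of early failures without requiring it.

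The trial-chair exception might seem to widen the gap. A blood-enrolled subject with no sample lacks a tissue result whether they respond or fail, so that loss is largely independent of outcome. Some subjects under the exception may already have a tissue result from pre-screening.

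Replacement is only implied, by enrolling to 7 and 18 evaluable subjects. Section 7.2 covers replacement according to the table of contents, but its text is not in the copy reviewed and may settle the matter. The type I error part depends on it.

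The FAS is primary for tumour response and needs no tissue result. That stands, but the go/no-go rule is written for evaluable subjects. The FAS also has its own way of losing early failures, through the exclusion for no post-baseline endpoint data, and that applies however HRAS was tested.

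There is also an effect in the other direction. A subject not confirmed in tissue but kept on treatment with the chair's agreement is not evaluable, even if responding.

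**Conclusion.** The point holds as a conditional one. For blood-enrolled subjects, the plan leaves an outcome-dependent way out of the go/no-go count. If their tissue goes untested after an early failure, the response rate can be inflated; if they are also replaced, so can type I error. A reader might conclude that alpha is in fact well above 0.089, but the documents do not show that. The upper figure of 0.165 needs, for example, every subject to be enrolled on blood and one in five to be lost untested. At 1% of treated subjects lost, alpha is 0.092, which is negligible. Every loss share is an assumption, as are the premises that all lost subjects are non-responders and all are replaced. With only 18 subjects, though, a single replacement is enough to matter, and the remedy is cheap. The change should be made, and it must also cover the FAS, because closing the tissue gap alone would leave the second exit for early failures open.

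**What to change.** 1. Where a sample has been confirmed as available, require it to be shipped before the first dose and tested whatever the subject's later course.
2. State that a treated subject enrolled on a positive HRAS result but with no tissue result stays in the denominator, as a non-responder unless a confirmed response is documented. This also covers subjects enrolled without a sample, whom earlier shipping cannot help.
3. Allow removal from the count only for a returned tissue-negative result, decided without knowledge of response.
4. Reconcile the Synopsis definition of evaluable with the FAS in Section 11.1.1, so that the go/no-go rule and the primary analysis use one denominator. Count treated subjects with no post-baseline endpoint data as non-responders instead of excluding them.
5. Check that Section 7.2 agrees with these rules.

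The cost is protocol and SAP wording, earlier shipment of an existing sample, and a possibly slightly lower observed response rate.
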